Study Protocol

IRB ID: 20180597 (CR00012479)

Study Number: 1 R34 DA043784-01A1

Date: July 19, 2018

Study Title

Culturally Modified Family Based Therapy for Haitian Youth in South Florida
(CIFFTA).

NCT number: 03876171

Date: July 19, 2018

INSTRUCTIONS:

1) Protocol Title

Culturally Modified Family Based Therapy for Haitian Youth in South Florida (CIFFTA).

2) IRB Review History*

None

3) Objectives*

The study will pursue the following Specific Aims:

Aim 1. To adapt CIFFTA and the assessment instruments necessary to test its efficacy to the unique Haitian sociocultural contexts. This process of adaptation has the purpose of optimizing CIFFTA's acceptability and cultural appropriateness. It will rely on ethnographic methods (participant observations, focus groups, and interviews) to guide the adaptation process.

Aim 2. Determine, via a pilot efficacy trial, the impact of CIFFTA compared with standard-of-care for reduction of drug use, risky sexual behaviors, and delinquency risk among Haitian adolescents ages 13 to 17 in Miami-Dade County. The ethnographic component of the study will monitor the delivery of the intervention, collecting process data, and affording the investigators needed perspective on the intervention's impact.

Aim 3. To generate preliminary data on the usefulness of assessment tools and CIFFTA's efficacy among the population. These data will help evaluate the effect of the intervention and its best form of implementation. They will also provide preliminary evidence to justify a full clinical trial of CIFFTA in a population of at-risk Haitian youth.

Primary study outcomes include: intervention attendance and completion; sustained abstinence in substance use through biochemical verification and self-report; family functioning; sexual risk behavior; and conduct disorder. Secondary outcomes include: recidivism in delinquency, improvement in family communication, and peer/gang involvement. Outcomes will be assessed through follow-up instruments at three points: 3, 6 and 12 months.

4) Background*

Despite preventive efforts made over the last three decades, it is clear that some populations have not benefited from attempts to deter them from risky behaviors. Haitian youth constitute an important but understudied population who may be particularly

Study Protocol

IRB ID: 20180597 (CR00012479)

Study Number: 1 R34 DA043784-01A1

Date: July 19, 2018

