This is a multi-wave study, with approximately all the participants recruited by the end of Year 02 and the remainder in the beginning of Year 03. At baseline, we will conduct comprehensive assessments of all study constructs and repeat all other assessments annually. Activities during the first three months will consist of the following: Staffing, Instrument Calibration, Ethnographic Update. Each wave will be composed of 22 participants to be randomized into two groups (11 each). Each undergo assessment at intake (T1) and outtake (T2), a booster session 3 months after outtake and a final assessment at 12 months. Data analysis process will be initiated at the third month and continue throughout the study implementation.

Study Protocol

[figure not shown]
IRB ID: 20180597 (CR00012479)

Study Number: 1 R34 DA043784-01A1

Date: July 19, 2018

Publications are expected to start from month 20. The table below details the activity processes.

Project Timeline

9) Study Endpoints*

Primary outcomes are: intervention attendance and completion; sustained abstinence in substance use through biochemical verification and self-report; family functioning; sexual risk behavior; and conduct disorder.

Secondary outcomes include recidivism in delinquency, improvement in family communication, and peer/gang involvement.

10) Procedures Involved*

RCT procedures

CIFFTA has three major components – Family-Based Therapy, Individual Therapy, and Psycho-educational Modules – delivered over 16 weeks in a six sessions (60 minutes each) per month format. In this study, the therapy will be delivered in the home to reduce missed sessions and premature termination. Special training will focus on how to structure the home environment to reduce distractions. Three sessions per month will typically be a session which may include Family-based Therapy or Psycho-educational modules with the family or parents alone (e.g., parent training). The other three sessions are typically with the adolescent alone and include Motivational Interviewing or Psycho-educational modules designed for the adolescent.

Study Protocol

IRB ID: 20180597 (CR00012479)

Study Number: 1 R34 DA043784-01A1

Date: July 19, 2018

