Focus Group. Focus groups will be guided by the following criteria: (a) they will be homogeneous with regard to age (parents or adolescents only); (b) they will follow a relatively structured interview guide with high involvement of the ethnographer as moderator; and (c) they will have six to ten participants each. Topical areas for the focus group will include the following: impact of the interventions; behavior changes of adolescents of parents; changes in the family.

Instrumentation.

The primary constructs for the youth participants will include: risk for re-offending, criminal history, patterns of drug/alcohol use, psychological adjustment, evidence of conduct disorder, family functioning, and acculturation. Constructs for the caregiver(s) will include their assessment of their child's conduct, family functioning, and their own level of acculturation. At baseline, information will also be gathered on participants demographic status. The instrument will be administered at participants' homes. Along with the demographic data, the baseline questionnaire will incorporate measures from the instruments described below, culminating in a unified tool taking no more than one hour to administer.

Behavioral, emotional, and academic functioning. We will administer standardized measures of youths' emotional and behavior disorders. Parent and youth reports on the Achenbach System of Empirically Based Assessment will assess youth's behavioral, emotional, and academic functioning. Parents will complete the Child Behavior Checklist (Achenbach 1983); and youth also will complete the parallel Youth Report Form (YRF). These measures yield scores for internalizing and externalizing problems and academic competence, and have DSM-5 scales for multiple problem areas: depression, anxiety, somatic, attention deficit/hyperactivity, oppositional, and conduct problems.

Risk for re-offending. Level of risk will be assessed with the Youth Level of Service/Case Management Inventory (YLS/CMI) developed by Hoge and Andrews (51) that screens for risk in eight domains (conduct disorder,

Study Protocol

IRB ID: 20180597 (CR00012479)

Study Number: 1 R34 DA043784-01A1

Date: July 19, 2018

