Family Functioning. Family functioning will be assessed by the Cohesion and Conflict Subscales from the Family Environment Scale [FES] (55). Family cohesion and conflict are specifically targeted because they have been found to be among the strongest predictors of youth problem behavior and these two scales have been found to capture much of the variability attributed to the FES (56). In prior work, the FES has demonstrated good internal consistency reliability ($\alpha = .93$ for adults and .94 for children) (55). We will also modify this instrument for adaptability to the Haitian immigrant context. As with the other instruments, reliabilities of the modified Family Functioning instrument will be ascertained for additional internal consistency and test-retest reliability as

Study Protocol

IRB ID: 20180597 (CR00012479)

Study Number: 1 R34 DA043784-01A1

Date: July 19, 2018

necessary. Parents' involvement in the day-to-day lives of their youth children will be further assessed with a 5-item paternal-child centeredness scale developed by Schaefer (57) that typically yields reliability coefficients in excess of .80.

The Bicultural Involvement Questionnaire, designed by Szapocznick (24) and adapted for use in Haitian populations by Jean-Gilles (58) measures the degree of comfort and enjoyment respondents receive from engaging in behaviors representative of the culture of origin (e.g. speaking the native language, consuming native food, listening to ethnic music) as well as behaviors representative of the host (U.S.) culture. Scores deriving from this measure include one for monoculturalism with respect to the native (Haitian) culture, and another for adaptation to the host (U.S.) culture. Szapocznick & Kurtines (24) report internal consistency coefficients of .93 and .89 for these scales on samples of 12 to 16 year old Hispanic youths. The internal consistency coefficients for the Creole version of the BIQ subscales were .72 for monoculturalism and .87 for Americanism, respectively.

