difference at a particular time between the two conditions (6). Following Cohen's guidelines (5), we will interpret our effect sizes using the convention of "small" ( $d = .2$ ), "medium" ( $d = .5$ ), and "large" ( $d = .8$ ).

Our hypotheses concerning the direct and indirect effects of key variables on drugs/alcohol use, risky sexual behavior, delinquent behavior, and recidivism will be tested using SEM mediation analyses. To test potential indirect relationships we will include several mediators, including family connectedness, acculturation (bicultural involvement scale), and motivation to change. This will allow us to examine whether CIFFTA directly effects our outcomes of interest and/or whether the effect of CIFFTA operates through its effect on family connectedness, acculturation, and motivation to change. These mediation models will enable us to address **Specific Aim #2** by testing the significance of paths in the model linking the intervention variable to the risk-related outcomes in question (both at discrete points in time and as the change index derived from differences in ordinal frequency at baseline and at post-intervention time intervals).

In a separate set of analyses, we will examine the hazard rate of drug/alcohol use and sexual risk behavior during the post-intervention phase of the study. Comparisons across the two intervention conditions will thus be made regarding the hazard rate of having sex during the post-intervention period, sex with multiple partners ( $>1$  per month), and unprotected sexual episodes. Specifically, shared frailty Cox proportional hazard regression will be utilized to examine possible differences in the hazard rate of various risky behaviors (drug- and sex-related) in CIFFTA and control conditions during the post-intervention phase. This will prove particularly helpful in determining the hazard rate for post-intervention sexual initiation or unprotected sex in the two groups being compared, while also controlling for the time-dependence nature of our data. Similar analyses will be performed regarding initiation into drug use and other problem behaviors to determine whether the possible benefits of the CIFFTA approach extend to a range of risky behaviors.

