**Analysis Rationale:** While there are numerous approaches to analyzing longitudinal data, including hierarchical linear models (HLM), we opted for a SEM approach since it provides greater modelling flexibility and better enables us to test our underlying theoretical model. In contrast to HLM, SEM allows for the simultaneous estimation of multiple growth curves, indirect/direct effects, and multiple indicators of model fit. Mediating relationships can be assessed within a HLM framework using Baron and Kenny's (10) approach, but SEM allows for the decomposition of direct/indirect effects as well as the simultaneous estimation of mediating and moderating relationships (11). Moreover, SEM will allow us to estimate growth-curves and mediating relationships at the same time in a way that HLMs cannot (12). The estimation of indirect effects within a growth-curve framework is especially important for **Specific Aim #2**, as we hypothesize that CIFFTA will not only have a direct effect on our outcome measures, but will also have an indirect effect operating through its effect on family connectedness, acculturation, and motivation to change. The estimation of mediating relationships will provide greater insights into any causal mechanisms (if any) at work, allowing for a more refined application of CIFFTA in a possible full clinical trial. SEM is also better equipped for assessing our theoretical model. In addition to providing measures of statistical significance, SEM generates several useful measures of overall model fit (e.g., CFI, AIC, BIC, etc.) that can be used to evaluate the appropriateness of our theoretical model over alternative models (11). Finally, SEM is better equipped to handle missing data than traditional regression or HLMs as it allows for maximum likelihood or Bayesian estimation (13).

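### The SAP tests motivation to change as a mediator, but no instrument in the protocol measures it; the secondary outcome family communication has neither an assigned instrument nor an analysis

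*SAP*

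**What the plan says.** **Mediator.** SAP, Analytic Methods, names the mediators for the SEM analyses as "family connectedness, acculturation (bicultural involvement scale), and motivation to change". Only acculturation is tied to a scale. The Analysis Rationale repeats the set as a hypothesis under Aim 2, expecting CIFFTA to have an "indirect effect operating through its effect on family connectedness, acculturation, and motivation to change". It adds that the mediation results should help refine how CIFFTA is applied in a full trial.

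**Constructs.** Protocol section 10, Instrumentation, opens its youth list with "The primary constructs for the youth participants will include: risk for re-offending, criminal history, patterns of drug/alcohol use, psychological adjustment" and closes it with "psychological adjustment, evidence of conduct disorder, family functioning, and acculturation". The caregiver list covers the child's conduct, family functioning and the caregiver's own acculturation. The baseline questionnaire is to be built from the instruments described there and is capped at one hour.

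**Family communication.** Protocol section 9 states: "Secondary outcomes include recidivism in delinquency, improvement in family communication, and peer/gang involvement". Section 3 gives the same three and adds: "Outcomes will be assessed through follow-up instruments at three points: 3, 6 and 12 months". On the family measures, section 10 states: "Family functioning will be assessed by the Cohesion and Conflict Subscales from the Family Environment Scale". A 5-item parent-child centeredness scale supplements these.

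**The concern.** An indirect effect needs a value of the mediator for each participant, in both arms, taken before the outcome it is meant to explain. If the protocol is followed as written, no such value exists for motivation to change, and an analyst cannot supply it after the data are in.

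The likely result is that the path is silently dropped, or that a motivation variable is assembled afterwards from items collected for another purpose. The SAP's Power Analysis section leaves room for the second course, because it allows several indicators to be combined by principal components into one scale. That would sit badly with the same section's commitment to a few theory-based pathways rather than exploratory ones. It also matters for Aim 3, which uses this pilot to judge the assessment tools and to justify a full trial.

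For family communication the stake is smaller: a declared secondary outcome that nobody is told how to score or analyse.

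**Working it through.** No power or sample-size figure bears on this point. The check is to set each variable against every instrument in protocol section 10.

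| Instrument | Stated use | Motivation to change? | Family communication? |
|---|---|---|---|
| Child Behavior Checklist and youth form | behavioural, emotional and academic functioning | not stated | not stated |
| YLS/CMI | re-offending risk, eight domains | not stated; has an attitudes/orientation domain | not stated; has a family circumstances domain |
| CASI | drug use, psychological adjustment, sexual risk and other areas | not stated | not stated; has a family/household relationships area |
| RBPC Conduct Disorder subscale | caregiver-rated disruptive behaviour, 22 items | no | no |
| Family Environment Scale, Cohesion and Conflict | family functioning | no | not stated |
| Parent-child centeredness scale | parental involvement, 5 items | no | not stated |
| Bicultural Involvement Questionnaire | acculturation | no | no |
| Urine screen | four drugs | no | no |

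**The three named mediators.**
- Acculturation has a named instrument.
- Family connectedness is plausibly covered by Cohesion, though neither document says so.
- Motivation to change has none. In the protocol it appears under the early treatment stage (weeks 1-3), as something motivational interviewing is meant to raise in the family. That is treatment content, not measurement. The SAP does not say whose motivation is meant, the youth's or the parent's.

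**Family communication.** No instrument is assigned to it. Nor does the SAP analyse it: its main outcomes are drug/alcohol use, risky sexual behaviour, delinquent behaviour and recidivism. Protocol section 12 lists family functioning among the outcome measures and does not list communication.

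**Effect of timing on repair.** Section 8 sets waves of 22, and 88 / 22 = 4, which agrees with the four waves in the SAP. If a scale were added only after wave 1 had passed intake, 3 × 22 = 66 of 88 participants (75%) could still be measured at both intake and outtake. The other 22 (25%) would lack an intake value but could still be measured at outtake if they had not reached it.

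**The case against.** Several replies have force.

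- **Most of the plan does not need these variables.** This stands. A reader might infer that the plan as a whole cannot be carried out, but the growth models, the shared-frailty Cox models and the acculturation path use neither variable.
- **Nearby measures may cover communication.** The CASI and YLS/CMI both have family domains. Item content is not in the documents, so one cannot say that nothing collected touches on communication. What can be said is that no measure is assigned. Nor does the SAP contain a communication analysis that would fail; it contains none.
- **The gap could be repaired after recruitment starts.** This stands in part. It is tempting to say that nothing can be done once wave 1 has enrolled, but three of four waves could still be measured in full. Under randomisation an intake value of a mediator improves precision and confounder control without being strictly required, and the SAP allows paths at discrete times. Only values from participants already past outtake would be lost.
- **Treatment records might serve as a substitute.** One might answer that standard-of-care youths would have none. The documents do not say that: protocol section 22 refers to standard-of-care therapists. Equally, they describe no motivation score derived from records in either arm.
- **Instruments are still being adapted under Aim 1, and the analyses are described as preliminary.** This limits the severity. However, the adaptation described concerns named instruments, none of them for motivation, and the ethnography is to inform interpretation without any stated scored variable.
- **The mediator list is introduced as open-ended.** True, so one of three counts only the mediators named.

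**Conclusion.** The point holds in a limited form. Motivation to change is a named mediator and an Aim 2 hypothesis with no construct or instrument behind it, so that one indirect effect, of three named, cannot be estimated from the data described. This is more than missing detail, because following the protocol would leave the data uncollected. The other planned analyses, including the comparison between arms, are unaffected.

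Family communication, one of three secondary outcomes, is a separate and lesser gap: no assigned instrument and no planned analysis.

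The conclusion assumes that the Instrumentation text is the full list of measures, which is how the protocol presents it. The opening part of the SAP and the timeline table in protocol section 8 could not be checked. A measure named there would change the finding.

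**What to change.** **Motivation to change.** Choose one:
1. Add one short self-report scale to the questionnaire in both arms at intake and outtake, ideally before wave 1. Name the scale and the respondent. An outtake value comes before the 3-, 6- and 12-month outcomes, since protocol section 10 counts those from the end of the intervention. The cost is a few minutes within the one-hour limit, plus an amendment.
2. Delete motivation to change from the mediation hypotheses in both SAP places, Analytic Methods and Analysis Rationale. The cost is wording only.

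**Family communication.** Assign a measure, respondent and time points, and add an analysis to the SAP, or remove it from protocol sections 3 and 9. Restating it as family cohesion and conflict is not a solution: those subscales already measure family functioning, a primary outcome, so one measure would become both primary and secondary.

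It would also help to state in one line which scale represents family connectedness.

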## **Major Analytic Methods Proposed (Including Statistical Design and Power)**

### ***Specific Aims***

**Aim 1.** To adapt CIFFTA and the assessment instruments necessary to test its efficacy to the unique Haitian sociocultural contexts. This process of adaptation has the purpose of optimizing CIFFTA's acceptability and cultural appropriateness. It will rely on ethnographic methods (participant observations, focus groups, and interviews) to guide the adaptation process.

**Aim 2.** Determine, via a pilot efficacy trial, the impact of CIFFTA compared with standard-of-care for reduction of drug use, risky sexual behaviors and delinquency risk among Haitian adolescents ages 13 to 17 in Miami-Dade County. The ethnographic component of the study will monitor the delivery of the intervention, collecting process data and affording the investigators needed perspective on the intervention's impact.

**Aim 3.** To generate preliminary data on the usefulness of assessment tools and CIFFTA's efficacy among the population. These data will help evaluate the effect of the intervention and its best form of implementation. They will also provide preliminary evidence to justify a full clinical trial of CIFFTA in a population of Haitian youth at risk.

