### ***Analytic Methods***

Latent Growth Modeling within a Structural Equation Model (SEM) framework. We will conduct latent growth curve analyses using Stata 14 gsem (1), SAS Proc Mixed (2), SPSS Mixed Models, and/or Mplus 8 (3) to compare the trajectories of participants in CIFFTA to those in TAU. Given that the data are balanced and have more than 2 time points, the model is identified, thereby allowing us to perform SEM growth curve analysis (4). These models conceptualize each component of growth (the baseline/intercept, the slope/rate of change, the quadratic slope, etc.) as composed of a fixed and random effect. Thus, these models have multiple components of variance as well as a regression-type model of the underlying mean growth curves of the two groups. Within an SEM framework, growth curves are treated as latent (unobserved) variables influenced by occasion- and individual-level covariates, allowing us to explicitly model growth trajectories overtime.

Specific analysis link functions will be matched to fit the distribution of each outcome variable. For ordinal outcomes (e.g., frequency of drug/alcohol usage), we will use an ordinal logistic regression function. The proportional odds assumption will be evaluated using the Brant test, and if needed, addressed by allowing problematic coefficients to vary across levels of the outcome variable. Count outcome measures (e.g., number of sexual partners, problem behaviors, re-arrests) will be analyzed using a negative binomial function rather than Poisson regression to address potential over-dispersion. Vuong tests will be performed to assess whether the data have an excess of zeros, and if necessary, zero inflated negative binomial regression will be used instead.

Analysis for Aims 2 and 3: The first set of analyses will explore the efficacy of CIFFTA compared to SOC in modifying the main adolescent outcomes and to generate effect sizes for a possible full clinical trial: a) drug/alcohol use, b) risky sexual behavior, c) delinquent behavior, and d) recidivism. Latent growth modeling will be used to investigate the efficacy of CIFFTA as compared to SOC. For each model, we will examine the effect sizes to determine the overall impact of CIFFTA over SOC on the outcome variables. We will generate estimates of effect sizes, such as Cohen's d (5), for both rate of change and for the

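### The SAP offers two routes to Aim 2 without saying which decides, and the one that carries a named significance test, paths in mediation models, does not measure impact versus standard of care

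*SAP*

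**What the plan says.** Aim 2 (SAP, Specific Aims) concerns "the impact of CIFFTA compared with standard-of-care for reduction of drug use, risky sexual behaviors and delinquency risk". This is a contrast between randomised arms. Protocol section 10 (Overview of Assessment Procedures and Attrition) commits to intention-to-treat.

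The SAP then gives two routes to Aim 2, both under Analytic Methods.

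- **Growth models.** "Analysis for Aims 2 and 3: The first set of analyses will explore the efficacy of CIFFTA compared to SOC", and "Latent growth modeling will be used to investigate the efficacy of CIFFTA as compared to SOC". No mediators are named for these models. The result is to be read as follows: "For each model, we will examine the effect sizes to determine the overall impact of CIFFTA over SOC on the outcome variables". Cohen's d is to be given for the rate of change and for the difference at a given time, and labelled small, medium or large. No test, interval or decision rule is stated.
- **Mediation models.** These add family connectedness, acculturation and motivation to change, to "examine whether CIFFTA directly effects our outcomes of interest and/or whether the effect of CIFFTA operates through its effect on family connectedness" and the other mediators. The SAP says they address Aim 2 "by testing the significance of paths in the model linking the intervention variable to the risk-related outcomes in question".

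The Analysis Rationale hypothesises that "CIFFTA will not only have a direct effect on our outcome measures, but will also have an indirect effect" through those three variables. It notes that "SEM allows for the decomposition of direct/indirect effects", and calls indirect effects within the growth-curve framework especially important for Aim 2.

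Shared frailty Cox models also compare the two conditions after the intervention. They name no mediators and are not tied to Aim 2 by name. Protocol section 12 (Data Management) says significance levels will be adjusted for multiple outcome measures. Neither document says which analysis settles Aim 2.

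**The concern.** Leaving aside the separate Cox comparisons, the only significance test that the SAP links by name to Aim 2 sits in models containing variables measured after randomisation. Two problems follow.

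- **The direct path is a different quantity.** It is what remains once the part carried by the mediators has been taken out. The SAP expects some of the benefit to be carried by them, so this path understates impact in the very case the investigators hope for.
- **The mediator-outcome link is not randomised.** Youths whose families become closer may differ in other ways that also affect drug use or re-arrest. That confounding enters the direct and the indirect path, but not the total effect.

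So a reader who relies on direct paths risks missing a real effect, and one who counts indirect paths risks declaring an effect that is not there. The answer can also change with the mediators entered. The Power Analysis section allows path analyses to be run separately, and the protocol's adjustment covers outcomes, not paths. The results are meant to support a larger trial, so a wrong answer would carry forward.

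**Working it through.** **Inputs.** From the documents: 80 analysed and R² = 0.05 (SAP, Power Analysis); equal arms, 11 and 11 per wave (Protocol section 8). Assumed, because the documents do not give them: two-sided 5% level, one mediator, a continuous outcome with within-arm SD 1, and the path sizes below.

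**Effect size.** Reading R² as the variance explained by arm, r = √0.05 = 0.2236 and d = 2r/√(1 − r²) = 0.4472/0.9747 = 0.459.

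**The SAP's own figure.** It states power of 0.84-0.86. A single-path F test with f² = 0.05/0.95 = 0.0526 and noncentrality 80 × 0.0526 = 4.21 gives 0.53. The stated power is not reproduced by this test. Repeated-measures versions give 0.61 to 0.97, depending on an assumed correlation. That is a separate matter. Here 0.53 serves only as the benchmark for the total-effect test.

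**Step 1: what the direct path loses.** The model is Y = c′X + bM + e, where X is arm and M the mediator, and the arm-to-mediator effect is a. The total effect is c′ + ab = 0.459. With b = 0.4 and mediated share s, a = s × 0.459/0.4. There were 4,000 simulated trials per row.

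| Share mediated | a | Total-effect test rejects | Direct path rejects |
|---|---|---|---|
| 25% | 0.29 | about 53% | 37% |
| 50% | 0.57 | about 53% | 19% |
| 75% | 0.86 | about 53% | 9% |
| 100% | 1.15 | about 53% | 5% |

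A second grid fixed a at 0.5 or 0.8 SD and let b vary (20,000 trials per case, same d). Direct-path power was 0.46-0.49 with nothing mediated, 0.16-0.20 at 50% and 0.05 at 100%. Total-effect power stayed at 0.52-0.53.

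**Step 2: reading the indirect path as well.** In the second grid, using a joint-significance test of the indirect path:

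| Share mediated | Total significant, direct not | Total significant, neither path significant |
|---|---|---|
| 50% | 0.33-0.36 | 0.06-0.08 |
| 100% | 0.50 | 0.004-0.03 |

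Reading both paths therefore recovers most of what the direct path misses.

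**Step 3: what the indirect path costs.** Suppose CIFFTA has no effect on the outcome and the mediator does not cause it. Suppose too that an unmeasured common cause gives a within-arm mediator-outcome correlation ρ of 0.3-0.4, while CIFFTA shifts the mediator by a = 0.5-0.8 SD. The fitted mediator coefficient is then ρ in expectation, the indirect effect is +ρa and the direct effect is −ρa. They cancel in the total: ρa − ρa = 0. The false effect on each path runs from 0.3 × 0.5 = 0.15 SD to 0.4 × 0.8 = 0.32 SD. Rejection rates by simulation:

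| Test | Rejects with no true effect |
|---|---|
| Total effect | about 5% |
| Direct path | about 11-29% |
| Indirect path | about 45-91% |

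With mediator and outcome both scored so that higher is better, the false indirect effect favours CIFFTA and the false direct effect goes against it.

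**The case against.** A reader might infer that Aim 2 is tested only through mediation paths. The documents do not support that. The SAP heads its growth-model comparison as the analysis for Aims 2 and 3, lists it first, and names no mediators for it. The Analysis Rationale mentions significance measures from SEM in general terms, and the protocol lists latent growth and mixed models for the outcomes, with intention-to-treat and an adjustment for multiple outcomes. The total-effect analysis is therefore planned. What it lacks is a stated test or interval, and priority over the mediation paths.

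A reader might also infer that a null direct path would be reported as no effect. No passage says so. The mediation analysis covers direct and indirect effects, and if CIFFTA works through family connectedness the indirect path is the one expected to show it. Step 2 bears this out, so the loss of power in Step 1 is not by itself the harm under the plan as written. That objection stands. It does not rescue the paths as a test of impact, because Step 3 shows that counting the indirect path gives up control of false positives.

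Two smaller objections also stand. The simulations use one mediator and a continuous outcome, whereas the SAP plans several mediators, ordinal and count outcomes, and growth curves. And the direct path does not always lose power. At d = 0.65, a = 0.5 and 75% mediated, its power was 0.87, because a mediator coefficient of 0.975 then explains 0.975² = 95% of the within-arm variance.

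**Conclusion.** The concern holds in this form: the SAP leaves open whether Aim 2 rests on growth-model effect sizes without a stated test, or on significance tests of mediation paths. The second route does not answer the Aim 2 question. Under the stated assumptions the direct path rejects in 37% down to 5% of trials where the total-effect test rejects in about 53%. With no true effect and a confounded mediator, the paths reject in 11-29% (direct) and 45-91% (indirect) of trials where the total-effect test holds about 5%.

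These sizes are illustrative, since path strengths and confounding are assumed. The direction does not depend on them: only the total effect keeps the protection of randomisation.

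This should be settled before analysis, but it is not a fatal flaw. The SAP calls its analyses preliminary and already plans the comparison that should decide.

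**What to change.** State in the SAP that Aim 2 is judged on the total CIFFTA-versus-SOC effect: the arm or arm-by-time term, with 95% CI, from the growth model without mediators, in all randomised youths. Choose the term in advance for each outcome, because the SAP now allows both a rate of change and a difference at a given time. Make one test per main outcome (drug and alcohol use, sexual risk, delinquency, recidivism), with the multiplicity adjustment that the protocol already promises.

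Keep the mediation models as secondary and explanatory. Report total, direct and indirect effects side by side, and state that the mediator-outcome link is not randomised. Reword the sentence that ties mediation paths to Aim 2, so that mediation explains the Aim 2 result and does not decide it. It need not be deleted.

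The cost is SAP wording only. No new data, youths or models are needed.
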